8.2. Key Definitions

Screening Period is a Period of approximately 2-4 weeks before Day 1/Baseline during which subject eligibility is evaluated and standardized background topical therapy is introduced over a run-in Period of at least 2 weeks before Day 1/Baseline.

The Initial Period is defined as Day 1/Baseline to Week 16 (before the Week 16 dose, with last dose at Week 12). If early discontinued during treatment period, it is defined as the period until 4 weeks after last dosing date or early termination date whichever is earlier.

The Maintenance Period is defined as Week 16 (Maintenance Baseline) to Week 48. If early discontinued during treatment period, it is defined as the period until 4 weeks after last dosing date or early termination date whichever is earlier.

Follow-up Period is defined as the post end of treatment period (i.e., 1 day after end of treatment period) to Follow-up visit in respective treatment period.

The Baseline value of the Initial Period will be taken as latest valid value prior to first injection of study drug. For subjects randomized but not treated, the Baseline value will be the latest value prior to the randomization. Week 16 measurements will serve as Baseline measurements for the Maintenance Period (i.e., Maintenance Baseline). If Week 16 measurements are missing for re-randomized subjects, the last valid non-missing measurement in the Initial Period (i.e., before the dosing for Maintenance Period at Week 16 visit) will be taken as the Baseline measurement for the Maintenance Period.

For diary data (e.g., Peak Pruritus (PP) NRS, Sleep disturbance (SD) NRS), the Baseline values will be the weekly prorated average of non-missing subject diary scores reported during the 7 days. A minimum of 4 daily scores out of the 7 days is required to calculate the weekly prorated average score. Refer the details for the analysis visit window for diary data in Section 8.4.

The date of first treatment is defined as the date of first injection of study drug. The date of first treatment is the Baseline date.

The date of last treatment is defined as the date of last injection of study drug.

Study day is defined as the number of days from the date of first treatment and will be calculated as follows:

This document is confidential.

- If the event date \geq date of first treatment, study day = event date – date of first treatment + 1. Study Day 1 is therefore defined as the day of first treatment.

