Exposure-adjusted incidence rates of TEAEs is defined as the number of subjects exposed to treatment and experiencing a certain event divided by the total time of all subjects who are at risk for the event. Specially, for subjects with no event the exposure time is the time from the first drug intake to the end of treatment period. Exposure years is calculated as last study drug exposure date minus first study drug exposure date plus one, divided by 365.25 which is the number of days count in a year. This exposure year calculated for each subject is then added cumulatively and is derived for each treatment arm. So each treatment arm will have one value for exposure years (aka. patient years). The exposure year calculation is different in case of subjects who have completed the study or discontinued from the study or having withdrawn from the study due to any reason. Only the event occurred during the treatment period will account for calculation.

Subject listings will be presented for all TEAEs, TEAEs of special interest, serious TEAEs, severe TEAEs, TEAE leading to permanent discontinuation of study drug, TEAEs leading to death and pre-treatment AEs. Subject listings of TEAEs for subjects with COVID-19 infection and adjudicated Asthma TEAEs will also be listed.

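### SAP 13.1 gives incompatible person-time rules for the exposure-adjusted TEAE rates, so the reported rate depends on which rule is programmed

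*SAP*

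**What the plan says.** The rates appear in Tables 14.3.1.4.1 (all causalities) and 14.3.1.5.1 (study drug related), both by SOC and PT. One paragraph of SAP 13.1 describes the denominator in three ways.

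- **Time at risk.** The number of subjects with the event is "divided by the total time of all subjects who are at risk for the event". A subject without it is followed to the period end: "for subjects with no event the exposure time is the time from the first drug intake to the end of treatment period".
- **Dosing span.** "Exposure years is calculated as last study drug exposure date minus first study drug exposure date plus one, divided by 365.25". These values are added up over the arm: "So each treatment arm will have one value for exposure years (aka. patient years").
- **By disposition.** "The exposure year calculation is different in case of subjects who have completed the study or discontinued from the study", and likewise for withdrawals. No formula follows.

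For the numerator, "Only the event occurred during the treatment period will account for calculation".

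SAP 8.2 runs the Initial Period to Week 16, with the last dose at Week 12, and the Maintenance Period to Week 48. For early discontinuers the period ends at the earlier of four weeks after the last dose and the early termination date. SAP 8.2 does not define the last exposure date used in the formula. The nearest defined term is in the sentence "The date of last treatment is defined as the date of last injection of study drug", and SAP 9.6 uses that term in a last-minus-first-plus-one calculation of treatment duration.

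**The concern.** A time-at-risk denominator stops counting a subject at the first occurrence of the event in question, so it changes from one SOC or PT row to the next. A single patient-years figure per arm does not. Both cannot be programmed, and the sentence on disposition cannot be programmed at all. Two programmers working independently could each follow the paragraph and report different rates.

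The dosing-span formula may bring a second problem. If its last exposure date is the last injection, the weeks between that injection and the end of the period can add events to the numerator while adding no time to the denominator.

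What is at stake is the absolute rate per 100 patient-years in two planned safety tables. SAP section 2 says planned analyses will go into regulatory submissions or manuscripts.

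**Working it through.** The documents state no patient-years or rate, so there is no figure to reproduce.

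**Inputs.** Target days come from SAP 8.4: Week 12 = Day 85, Week 16 = Day 113, Week 44 = Day 309, Week 48 = Day 337. The last injections, at Week 12 and Week 44, come from SAP 4.5. Protocol 8.4 counts placebo as study drug, so the Week 44 placebo injection in the Q8W group is a study drug injection and all Maintenance groups have the same dosing span.

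**1. Formula read as last injection, against full period time (on-schedule completer).**

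| Span | Formula (days) | Full time (days) | Rate multiplier |
|---|---|---|---|
| Initial | 85 − 1 + 1 = 85 | 113 − 1 + 1 = 113 | 113/85 = 1.33 |
| Maintenance | 309 − 113 + 1 = 197 | 337 − 113 + 1 = 225 | 225/197 = 1.14 |
| Both as one span | 309 − 1 + 1 = 309 | 337 − 1 + 1 = 337 | 337/309 = 1.09 |

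The gap is 28 days in each row. In a combined span it is lost once, because the Week 16 dose bridges Weeks 12 to 16.

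**2. Same reading, against time at risk.** Assume onset at mid-period (day 57 of 113; day 113 of 225). With incidence p, mean time at risk = (1 − p) × full + p × mid.

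- Initial: 110.2, 107.4 and 101.8 days at 5%, 10% and 20%. Divided by 85, this gives 1.30, 1.26 and 1.20.
- Maintenance: 219.4, 213.8 and 202.6 days. Divided by 197, this gives 1.11, 1.09 and 1.03.

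**3. Formula read as ending at the end of the treatment period (Initial).** The only difference left is event censoring: 110.2/113 = 0.975, 107.4/113 = 0.950, 101.8/113 = 0.901. Rates are about 2.5%, 5% and 10% too low.

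**4. The three results side by side, Initial Period, 10% incidence.**

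- Last injection: 0.10 × 36525/85 = 43.0 per 100 patient-years.
- Time at risk: 0.10 × 36525/107.4 = 34.0.
- One value to period end: 0.10 × 36525/113 = 32.3.

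**5. Comparison between arms.** Within one period, with assumed incidences of 10% and 5%, a fixed denominator gives a rate ratio 107.4/110.2 = 0.975 times the time-at-risk ratio, that is 2.5% lower. In a combined span, take the protocol's planned 190 nemolizumab and 26 placebo maintenance subjects. Assume 500 and 250 subjects all on schedule, grouped by initial arm, and the last-injection reading. The multipliers against full time are:

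- Nemolizumab: (310 × 113 + 190 × 337)/(310 × 85 + 190 × 309) = 99060/85060 = 1.16.
- Placebo: (224 × 113 + 26 × 337)/(224 × 85 + 26 × 309) = 34074/27074 = 1.26.

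**6. The 28 days is the on-schedule value only.** Visit windows allow (113 + 5) − (85 − 5) = 38 days. A missed Week 12 dose gives 113 − 57 = 56. The eight-week COVID-19 delay of Week 16 in Protocol Appendix 2 gives (113 + 56) − 85 = 84. An early termination visit shortens the gap. A subject with one dosing visit contributes 1 day by the formula, against up to 29 days by SAP 8.2.

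**The case against.** The strongest reply is that the 28-day gap may not exist. The SAP has a defined term for the last injection and does not use it in this formula. The sentence just before the formula ends exposure at the end of the treatment period, and the formula may be no more than the arithmetic for that sentence. The remark on disposition may likewise only recall that end dates differ, and SAP 8.2 supplies those dates. The tables are also descriptive, and within a period the between-arm ratio hardly moves.

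Much of this stands. Reading the last exposure date as the last injection is an inference from SAP 8.2 and 9.6. The disposition sentence needs a cross-reference more than a rule of its own. The conflict itself remains on either reading: event-specific time at risk cannot yield one value per arm.

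Three stronger conclusions may tempt a reader, and the documents do not support them.

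- **That all rates are overstated by about a third.** Step 3 shows the opposite sign on the other reading. Even on the last-injection reading, the incidence above which the formula starts to understate depends on onset. In the Initial Period it is 28/56 = 50% with mid-period onset, 28/98 = 28.6% with onset at day 15, and never reached with onset at day 99 (28/14 exceeds 1). In Maintenance it runs from 28/196 = 14.3% (day 29) to 28/28 = 100% (day 197). The plan gives no TEAE incidences or onset times.
- **That 28 days are lost in every period.** SAP section 13 points to presentation by period. SAP 13.1 and the two table titles refer to the treatment period, which 13.1 describes as including both Initial and Maintenance. A single combined span is therefore possible.
- **That the safety comparison between arms is biased.** Within a period the shift is small. Unequal inflation arises only if the periods are combined, and the plan does not settle that.

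**Conclusion.** The paragraph contradicts itself and should be corrected. That conclusion needs no assumption beyond the wording of SAP 13.1.

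The size is conditional. With the last-injection reading, presentation by period and on-schedule completion, rates are up to 1.33 times (Initial) and 1.14 times (Maintenance) those on full period time. In one combined span the figure is 1.09 times for a subject completing both periods, and inflation could then differ between arms. If the formula ends at the period end, Initial Period rates are about 2.5% to 10% too low at 5% to 20% incidence with mid-period onset assumed. The direction therefore depends on the reading, the incidence and the onset time, and no single correction factor would repair the tables afterwards.

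The effect is confined to two descriptive tables. The co-primary and key secondary inference and the crude TEAE incidences do not use this denominator.

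**What to change.** For each SOC and PT, define person-time in SAP 13.1 as

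(earlier of the first occurrence of that event and the end of the treatment period per SAP 8.2 − first study drug injection of the analysed period + 1) / 365.25.

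This keeps the day-count convention and the year conversion, which are stated for these rates only in the formula being replaced. Remove the last-minus-first rule and the one-value-per-arm rule. Replace the sentence on disposition with a reference to the period ends in SAP 8.2. State in 13.1 whether these rates are shown separately for Initial and Maintenance or combined, and for which treatment groups. SAP 9.6 needs no change, since it describes treatment duration and not time at risk.

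The cost is SAP wording and one derived variable. The one downside is a separate denominator for each row of the tables.

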13.2. Laboratory Evaluations

13.2.1. Clinical Laboratory Evaluations

The hematology laboratory analyses, clinical chemistry laboratory analyses, and urinalyses will be performed at a central laboratory. Reference ranges will be supplied by the central laboratory and used by the investigator to assess the laboratory data for clinical significance and pathological changes. Reference ranges will be provided in the laboratory manual.

The following parameters will be reported for laboratory data.

- **Hematology:** Hemoglobin, hematocrit, white blood cell (WBC) count (with differential including eosinophils), red blood cell (RBC) count, platelet count, and mean cell volume (MCV).
- **Chemistry:** Creatinine, aspartate aminotransferase (AST), alanine aminotransferase (ALT), gamma glutamyltransferase (GGT), alkaline phosphatase, lactate dehydrogenase (LDH), total bilirubin, direct bilirubin, creatinine phosphokinase ([CPK], CPK isoenzyme test will be performed only if CPK is

This document is confidential.

elevated to $> 2.5 \times \text{ULN}$), albumin, total protein, uric acid, sodium, potassium, calcium, chloride, glucose, urea, total cholesterol, triglycerides, low-density lipoprotein (LDL), and high-density lipoprotein (HDL). Follicle-stimulating hormone (FSH) will be collected for postmenopausal subjects.

- **Urinalysis:** pH, glucose, ketones, blood, protein, leukocytes, nitrites, bilirubin, urobilinogen, and specific gravity.

Laboratory assessments are performed at Screening, Baseline, Week 8, Week 16, Early Termination and Follow-up during the Initial Period.

Laboratory assessments are performed at Week 32, Week 48, Early Termination and Follow-Up during the Maintenance Period.

Hematology and chemistry laboratory data (absolute values and change from Baseline; and change from Week 16 for Maintenance Period) will be summarized as continuous variables (scheduled visits only) for the Initial Period and the Maintenance Period. Urinalysis laboratory data will be summarized by visit (scheduled visit only). Last post-baseline, worst post-baseline and maximum post-baseline results will also be included and will include unscheduled visits in the derivation. And worst post-baseline value will be defined as the highest or lowest value relative to the reference range during the respective treatment Period.

Shift tables will be generated using the reference ranges (Low, Normal, High and Missing) for hematology and chemistry laboratory data. The number and percentage of subjects shifting from reference ranges between Baseline and each visit (scheduled visits only) will be summarized for the Initial Period and the Maintenance Period. In addition, shift table from Week 16 will be provided for the Maintenance Period. Last, worst and maximum post baseline values will also be included in the shift tables and will include unscheduled visits in the derivation. Worst post baseline value will be defined as the highest or lowest value relative to the reference range.

Summary of the number and percentage of subjects who met criteria of potential clinically significant (CS) value will be summarized (scheduled visits only) for hematology and chemistry laboratory data. Last, worst and maximum post-baseline results will also be included in the summary. Potentially CS ranges for adult and adolescent are listed in sections 22.3 and 22.4.

For statistical and graphical summaries of the laboratory tests, values below or above the limit of detection (e.g. ' < 3 ' or ' > 500 ') are substituted with the lower limit of detection minus 1% for values below the lower limit and are substituted with the upper limit of detection plus 1% for values above the upper limit (e.g. ' < 3 ' is substituted by ' 2.97 ', ' > 500 ' is substituted by ' 505 '). In data listings, the values are shown including the $<$ or $>$ sign.

Distribution of Aspartate Aminotransferase (AST), Alanine Aminotransferase (ALT), Alkaline Phosphatase (ALP), Total bilirubin and Creatinine Phosphokinase (CPK) will be displayed graphically as boxplot by treatment group for each scheduled visit and the maximum post-Baseline (including unscheduled visits in the derivation) values for the Initial Period and the Maintenance Period.

By-subject listing will be presented for all laboratory data. By-subject listing for subjects with at least one abnormal result (out of reference range) will be provided for hematology and clinical chemistry. By-subject listing for subjects with at least one potentially CS result will be provided for hematology and clinical chemistry.

This document is confidential.

All laboratory data will be listed for the Safety population.

13.2.2. Pregnancy Testing

All women of childbearing potential will have a serum pregnancy test at the screening visit and urine pregnancy tests (UPTs) at Baseline, Week 4, Week 8, Week 12 and Week 16, Early termination visit, and Follow-up of the Initial Period. UPTs will also be performed at Week 20, Week 24, Week 28, Week 32, Week 36, Week 40, Week 44, and Week 48, Early termination visit, and Follow-up of the Maintenance Period. Pregnancy test results must be available prior to the administration of the study drug.

All confirmed pregnancy test results, premenses status and childbearing potential assessment results will be listed on the Safety population.

13.2.3. Virology and TB Testing

Virology including HBsAg, HBcAb, hepatitis C, HIV-1, and HIV-2 antibody will be assessed at the screening visit. Subjects with a positive HBcAb and a negative HBsAg will also be assessed for hepatitis B surface antibody.

All virology results will be listed on the Safety population.

Subjects will be assessed for TB infection with a QuantiFERON-TB Gold test at the screening visit.

All TB test results will be listed on the Safety population.

13.3. Vital Signs

Vital signs will include pulse rate, systolic and diastolic blood pressure (after the subject has been sitting for at least 5 minutes) and body temperature.

Vital signs will be collected at the Screening visit and at Baseline, Week 4, Week 8, Week 12 and Week 16, Early termination visit, and at Follow-up of the Initial Period. Vital signs will also be collected at Week 20, Week 24, Week 28, Week 32, Week 36, Week 40, Week 44, Week 48, Early termination visit, and at Follow-up of the Maintenance Period.

Height and weight will be measured at Screening for all subjects. Height assessments will be conducted for adolescent subjects (aged 12-17) at Week 8 and 16 of the Initial Period, as well as Week 24, Week 32, Week 40, and Week 48 of the Maintenance Period and at Follow-up. Weight assessments will be conducted for adolescent subjects at Baseline, and Week 16 of the Initial Period as well as at Week 32, and Week 48 of the Maintenance Period and at Follow-up.

All vital signs including height and weight (absolute values and change from Baseline; and change from Week 16 for Maintenance Period) will be summarized as continuous (scheduled visits only) for the Initial Period and the Maintenance Period. Last post-Baseline results (including unscheduled visits in the derivation) will also be included.

The number and percentage of subjects who met criteria of potential CS value for vital signs and weight will be summarized (scheduled visits only) for the Initial Period and the Maintenance Period. Last post-Baseline results (including unscheduled visits in the derivation) will also be included.

This document is confidential.

Distribution of pulse rate, systolic and diastolic blood pressure will be displayed graphically as boxplot by treatment group for each scheduled visit and maximum post-Baseline (including unscheduled visits in the derivation) values for the Initial Period and the Maintenance Period.

By-subject listing of subjects with potentially CS vital signs and weight will be provided.

Potentially CS ranges for adult and adolescent are in sections 22.3 and 22.4.

13.4. ECG

A 12-lead Electrocardiogram (ECG) will be performed and read centrally at Screening, Week 16, Week 48, Early termination visit, and at Follow-up.

The overall results of the ECGs recorded as 'Normal', 'Abnormal, NCS' or 'Abnormal, CS' will be summarized by treatment group and visit (scheduled visits only) for the Initial Period and the Maintenance Period. Clinical significance will be determined by the investigator.

13.5. Physical Examination

A complete physical examination will include assessments of the head, ears, eyes, nose, throat, neck (including thyroid), skin/integumentary system, cardiovascular system, respiratory system, gastrointestinal system, musculoskeletal system, lymph nodes, nervous system, and extremities.

A physical examination will be performed at Screening, Baseline, Week 4, Week 8, and Week 16 of the Initial Period. Physical examination will also be performed at Week 24, Week 32, Week 40, and Week 48 of the Maintenance Period, as well as at Early termination visit, and at Follow-up.

The number and percentage of subjects with physical examination results classified as 'Normal', 'Abnormal, not Clinically Significant (NCS)' or 'Abnormal, CS' will be summarized (scheduled visits only), and body system for the Initial Period and the Maintenance Period.

Shift from Baseline of the physical examination category will also be summarized by body system for the Initial Treatment Period and shift from Baseline and from Week 16 will be summarized for the Maintenance Period.

By-subject listing will be provided for subjects who have at least one abnormal results from any body system or who missed the assessment due to any reason.

13.6. Respiratory Assessments

13.6.1. Respiratory Examination and PEF Testing

A respiratory examination consisting of questions regarding medical history of asthma, wheeze, dyspnea, and cough, will be performed for all subjects at Screening, Baseline, Week 4, Week 8, Week 12 and Week 16 of the Initial Period and at Week 20, Week 24, Week 28, Week 32, Week 36, Week 40, Week 44, and Week 48 of the Maintenance Period, as well as at Early termination visit, and at Follow-up.

Respiratory examination questionnaire results will be listed on the Safety population.

PEF testing will be performed for all subjects at Screening, Baseline, Week 4, Week 8, Week 12 and Week 16 of the Initial Period and at Week 20, Week 24, Week 28, Week 32, Week 36, Week 40, Week 44, and Week 48 of the Maintenance Period, as well as at Early termination visit, and at Follow-up.

This document is confidential.

PEF (absolute values and change from Baseline; and change from Week 16 for the Maintenance Period) will be summarized as a continuous variable (scheduled visits only) for the Initial Period and the Maintenance Period. PEF will be summarized separately for the subset of subjects with, and without, a history of asthma.

The number and percentage of subjects with PEF < 80% will be summarized by treatment group, visit (scheduled visits only), and medical history of asthma (with and without history of asthma) for the Initial Treatment Period and the Maintenance Period.

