^p PEF testing will be performed for all subjects at screening, baseline, Week 8, 16, 32, 48, and follow up visits. For subjects reporting a medical history of asthma, PEF testing (and ACT) will be performed at all visits during the clinical study. For subjects diagnosed with de novo asthma, PEF testing (and ACT) will be performed at all visits, starting with the visit in which the diagnosis was confirmed. Subjects should be asked to withhold asthma medication on study visit days until after PEF testing is complete, to the extent it does not pose an undue risk to the subject.

^q Complete PE should be performed at designated visits.

^r Contraceptive counseling should occur at screening or at applicable visits when pre-pubertal subjects begin menses.

^s Height collection will be performed for all subjects at screening. Height collection is only required for adolescents (ages 12-17) at designated post-screening visits.

^t 12-lead ECGs should be performed in the supine position, before any scheduled vital sign measurements and blood draws.

^u Vital signs will include pulse rate, systolic and diastolic blood pressure (after the subject has been sitting for at least 5 minutes), and body temperature.

^v At scheduled visits with laboratory, PK, and ADA assessments, samples are to be collected before study drug injection(s). See hematology, clinical chemistry (including FSH for postmenopausal subjects), and urinalysis testing details, respectively.

^w TB screening: QuantiFERON-TB Gold test for all subjects.

SAP Version: Final Version 1.0, 09-Nov-2022

Controlled Document ID: **3903A.01**, Effective Date 31-Aug-2020

Filing requirements: TMF

CONFIDENTIAL

Statistical Analysis Plan for Interventional Studies

Sponsor: Galderma Research & Development, LLC; Protocol No.: RD.06.SPR.118161

^x Only for WOCBP. Pregnancy test results must be available prior to the administration of the study drug. Serum pregnancy test to be performed at the screening visit; UPT at all other visits. For prepubertal subjects, reconfirm pre-menses status at every visit and, in case of status change, collect information on contraceptive measures and perform a UPT according to the schedule for WOCBP.

^y For postmenopausal subjects (i.e., no menses for 12 consecutive months), confirm status with a high FSH level in the postmenopausal range. Blood chemistry sample at the screening visit (V1) will also be used for an FSH test for the confirmation of postmenopausal status.

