9.3. Medical History

Medical history will be collected only at screening and will be coded using Medical Dictionary for Regulatory Activities (MedDRA, Version 25.0, March 2022).

Medical history will be summarized by treatment group and period. The summary will include number and percentage of subjects reporting each system organ class (SOC) and preferred term (PT) and will be sorted alphabetically by SOC and descending frequency of PT within SOC in the Nemolizumab 30mg Q4W group. Summary tables will be presented for the ITT population.

Medical history data listings will be presented by subject number, period, start date, stop date, SOC, and PT for the ITT population.

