17.2.5.2. Table Conventions

- Units will be included where available
- If the categories of a parameter are ordered, then all categories between the maximum and minimum category are presented in the table, even if n=0 for all treatment groups in a given category that is between the minimum and maximum level for that parameter. For example, the frequency distribution for symptom severity would appear as:

Severity Rating	n
severe	0
moderate	8
mild	3

Where percentages are presented in these tables, zero percentages will not be presented and so counts of 0 will be presented as 0 and not as 0 (0%).

This document is confidential.

- If the categories are not ordered (e.g., Medical History, Reasons for Discontinuation from the Study, etc.), then only those categories for which there is at least 1 subject represented are included.
- An Unknown or Missing category are added to each parameter for which information is not available for 1 or more subjects.
- Unless otherwise specified, the estimated mean, median, Q1 and Q3 for a set of values are printed out to 1 more significant digit than the original values, and standard deviations are printed out to 2 more significant digits than the original values. The minimum and maximum should report the same significant digits as the original values. Missing descriptive statistics or p-values which cannot be estimated are reported as “-”.
- Percentage values are printed to one decimal place, in parentheses with no spaces, one space after the count (e.g., 7 (12.8%), 13 (5.4%)). Pre-determine how to display values that round down to 0.0. A common convention is to display as '<0.1', or as appropriate with additional decimal places. Unless otherwise noted, for all percentages, the number of subjects in the analysis population for the treatment group who have an observation will be the denominator. Percentages after zero counts should not be displayed and percentages equating to 100% are presented as 100%, without decimal places.
- Tabular display of data for medical history, prior/concomitant medications, and all tabular displays of adverse event data are presented by the body system, treatment class, or SOC. The body system, drug class and SOC are displayed in alphabetically order. Within body system, drug class and SOC, preferred term will be display in descending frequency. If incidence for more than 1 preferred term is identical, they should then be sorted alphabetically.

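### SAP 13.6.1 says everyone has PEF at every scheduled visit; the schedule tests everyone at only some of them, so by-visit PEF tables change population at eight visits

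*SAP*

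**What the plan says.** SAP 13.6.1 gives the PEF schedule as "PEF testing will be performed for all subjects at Screening, Baseline, Week 4, Week 8, Week 12 and Week 16 of the Initial Period" and then names every Maintenance visit from Week 20 to Week 48, early termination and follow-up.

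SAP section 4.6 (Table 4-3, note p) gives a different one: "PEF testing will be performed for all subjects at screening, baseline, Week 8, 16, 32, 48, and follow up visits". It adds two groups who are tested more often. The first is subjects who enter with asthma: "For subjects reporting a medical history of asthma, PEF testing (and ACT) will be performed at all visits during the clinical study". The second is those who receive a new diagnosis, and here testing runs from the point of confirmation onward: "For subjects diagnosed with de novo asthma, PEF testing (and ACT) will be performed at all visits". Protocol 8.1.2 carries the same note, and protocol 9.2.9.3 agrees with it. Note d to the same tables has subjects who stop early complete the Week 16 or Week 48 assessments, so early termination is also an all-subject PEF occasion.

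For reporting, 13.6.1 plans PEF values and changes by scheduled visit, and then: "PEF will be summarized separately for the subset of subjects with, and without, a history of asthma". It also says: "The number and percentage of subjects with PEF < 80% will be summarized by treatment group, visit (scheduled visits only"), and by medical history of asthma. SAP Tables 14.3.4.4.6 to 14.3.4.4.13 deliver these outputs. Under the table conventions in SAP 17.2.5.2, "the number of subjects in the analysis population for the treatment group who have an observation will be the denominator" unless otherwise noted.

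**The concern.** The SAP describes PEF as complete at every visit, and the by-visit tables are laid out on that footing. If collection follows the schedule, a row labelled as all subjects holds the whole trial at Week 8, only asthma subjects at Week 12, and the whole trial again at Week 16. A mean or a PEF < 80% percentage can then move between visits because the people tested have changed, with no change in anyone's lung function.

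The no-history rows are more exposed. At the eight restricted visits a subject without an asthma history is due for PEF only after a new asthma diagnosis. Under protocol 9.2.9.4, a decline in respiratory assessments, PEF included, is one trigger for specialist referral in these subjects. Those who remain in the row may therefore be there partly because of a poor PEF. Newly diagnosed asthma is an adverse event of special interest (protocol 9.2.1.1), so a reader is likely to look at these rows. The 13.6.1 wording would also make subjects who were never due for testing look like missed assessments.

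**Working it through.** The plan gives no figure to reproduce. The check compares the two schedules and then follows the result into the tables.

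**Step 1: the two visit sets.**
- SAP 13.6.1, all subjects: screening, baseline, Weeks 4, 8, 12, 16, 20, 24, 28, 32, 36, 40, 44, 48 and follow-up. That is 15 scheduled visits (early termination set aside).
- Note p, all subjects: screening, baseline, Weeks 8, 16, 32, 48 and follow-up. That is 7.
- Difference: 15 − 7 = 8, namely Weeks 4 and 12 in the Initial Period and Weeks 20, 24, 28, 36, 40 and 44 in Maintenance.
- Of the 12 post-baseline visits through Week 48, 4 are all-subject visits and 12 − 4 = 8 are restricted.

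The PEF row of the schedule agrees: the cells flagged with note p, in both documents, are exactly these eight.

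**Step 2: is it a declared change?** SAP section 15 lists one departure from the protocol, the definition of concomitant medication. It says nothing on PEF. The 13.6.1 visit list matches the respiratory-examination list just above it, which does apply to everyone. SAP 13.6.2, on the Asthma Control Test, does limit testing to subjects with an asthma history or a new diagnosis.

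**Step 3: who is in each row at the eight visits.**
- With history: due for PEF at every visit. Complete.
- Overall: subjects with history plus new cases.
- Without history: new cases only, if they stay in this group. The SAP does not say so outright. The inference rests on SAP 9.3: "Medical history will be collected only at screening".
- Early-termination values do not fill the gaps, because SAP 8.4 does not window safety data.

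**Step 4: rough size of the no-history rows.** Planned numbers come from the documents: 750 subjects randomised 2:1, so 500 and 250; 190 nemolizumab subjects in Maintenance, so 190/3 ≈ 63 per re-randomised arm; and 26 on placebo. Two inputs are assumptions found in neither document: a no-history share of 60% to 80%, and new asthma in 0.5% to 3% of those subjects, all diagnosed before the visit in question. Dropout within each period is ignored.

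n at an all-subject visit = N × share; n at a restricted visit = N × share × new-asthma rate.

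| Group | N | All-subject visit | Restricted visit |
|---|---|---|---|
| Nemolizumab, Initial | 500 | 300 to 400 | 1.5 to 12 |
| Placebo, Initial | 250 | 150 to 200 | 0.75 to 6 |
| Each re-randomised arm | 63 | 38 to 51 | 0.2 to 1.5 |
| Placebo, Maintenance | 26 | 16 to 21 | 0.1 to 0.6 |

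For example, 500 × 0.6 × 0.005 = 1.5 and 500 × 0.8 × 0.03 = 12. Across the whole assumed range the restricted rows are a handful of subjects or none.

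**The case against.** A reader might infer that the PEF tables would mislead on the drug's main asthma signal. The documents do not support that. The phase 2b increase in asthma flares was in subjects with pre-existing asthma (protocol 6.2.3 and 6.3). They are due for PEF at every visit and have their own tables, so those rows are sound. The affected rows bear on newly diagnosed asthma and on the overall summary. New asthma is also covered by the special-interest event tables, the committee-adjudicated events, the full PEF listing and the listing of subjects whose PEF or ACT drops by at least 15%.

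A reader might also infer that the no-history rows at these visits contain nothing but new asthma cases. That goes beyond the text. If a new diagnosis moves a subject to the other group, the row is empty rather than selective. SAP 13.6.1 has the respiratory examination ask about asthma history at every visit, which leaves that possibility open. Off-schedule measurements could add other subjects. So could the COVID-19 guidance in protocol Appendix 2, which mentions PEF for all subjects, though in accordance with the protocol, and does not restrict PEF in its list of remote assessments.

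Other mitigations stand. The testing rule is the same in both arms, so an overall comparison at Week 12 is largely asthma subjects against asthma subjects. Change from baseline is within-subject and less exposed than absolute values. Continuous summaries print n (SAP 8.1), and SAP 17.2.5.2 asks for care with denominators and for explanatory footnotes. No hypothesis test on PEF is planned.

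These points limit the harm but leave the contradiction in place. The general advice on denominators helps little when 13.6.1 itself indicates that everyone was tested.

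**Conclusion.** The contradiction is certain: SAP 13.6.1 disagrees with the SAP's own schedule and with the protocol on who has PEF at eight of the 12 post-baseline visits through Week 48. It reaches the planned tables, because the denominator is subjects observed. The overall PEF and PEF < 80% rows would alternate between two populations. The no-history rows at those visits would be near-empty or consist mainly of new asthma cases. The second statement assumes that collection follows note p and that asthma history is fixed at screening.

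This is a minor reporting defect. Data collection, the rows for subjects with an asthma history and every efficacy conclusion are untouched. The documents give no basis for putting a figure on the distortion in PEF < 80%; only the count of visits is firm, and the row sizes are illustrative.

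**What to change.** - Reconcile the visit list in SAP 13.6.1 with note p of Table 4-3 and of protocol 8.1.2.
- Limit the overall and no-history by-visit PEF and PEF < 80% summaries to the occasions when all subjects are tested: baseline, Weeks 8, 16, 32 and 48, with early termination and follow-up as applicable.
- Show Weeks 4, 12, 20, 24, 28, 36, 40 and 44 only for subjects with an asthma history.
- State which history group newly diagnosed subjects belong to, and list them separately.
- Footnote each PEF table with who was due for testing at each visit.

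The cost is a correction to one SAP section, a table filter, a short listing and footnotes. No trial procedure and no data collection changes.
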